2.4 Primary Endpoint

The overall response rate (ORR) in subjects with metastatic castration resistant prostate cancer whose tumors harbor a genomic change resulting in CDK12 loss of function and who are treated with nivolumab and ipilimumab combination therapy followed by nivolumab monotherapy, or nivolumab monotherapy only (for applicable cohorts), as measured by PSA 50% decline from baseline as determined by PCWG3 criteria.

2.5 Secondary Endpoints

- 2.5.1 The overall response rate (ORR) in patients with metastatic non-prostate cancer harboring loss of CDK12 function, who are treated with nivolumab and ipilimumab combination therapy followed by nivolumab monotherapy, or nivolumab monotherapy only, as measured by RECIST 1.1 criteria.
- 2.5.2 The frequency and severity of adverse events, as assessed by CTCAE version 4.03 criteria, in patients with metastatic cancer harboring loss of CDK12 function treated with nivolumab and ipilimumab combination therapy followed by nivolumab monotherapy, or nivolumab monotherapy only.,
- 2.5.3 Assess the radiographic progression-free survival (rPFS), progression-free survival (PFS), duration of response (DOR) among responders, duration of therapy (DOT), time to progression (TTP), overall survival (OS) and objective tumor response in patients with measurable disease by RECIST 1.1 criteria. For subjects with metastatic CRPC, determine the PSA progression-free survival and time to PSA progression by PCWG3 criteria.
- 2.5.4 Measure the Quality of Life (QoL) in subjects treated on protocol therapy using EORTC-QLQ-C30 and BPI-SF.

2.6 Exploratory Endpoints

- 2.6.1 Tumor genome profiling by integrated DNA and RNA sequencing (including molecular tumor burden assessment) at baseline and optionally at progression.

2.6.2 Profiling of immune infiltration in tumor biopsies.

3.0 PATIENT ELIGIBILITY

Subjects must meet all of the inclusion and exclusion criteria to be enrolled to the study. Study treatment may not begin until a subject is enrolled.

3.1 Inclusion Criteria

- 3.1.1 Age \geq 18 years and ability to understand and the willingness to sign a written informed consent.
- 3.1.2 ECOG Performance Status of 0, 1 or 2.
- 3.1.3 Subjects must have histologic or cytologic or radiologic evidence of metastatic adenocarcinoma of the prostate without small cell histology OR another type of metastatic carcinoma. Radiologic or pathologic evidence of metastases is allowed.
- 3.1.4 All subjects, regardless of cancer type, must have a documented CDK12 loss on a CLIA approved, Next Generation Sequencing assay (tissue, cell-free DNA or other is allowed) and is willing to provide archival tissue for analysis. CDK12 loss will be confirmed by the IND Sponsor (at the University of Michigan) and may include deleterious mutations (e.g truncating mutation, inactivating missense mutation), rearrangement or deletion. Because it is not always stated explicitly in all NGS platforms/assays, the Sponsor Investigator will determine which genomic aberrations constitute CDK12 loss. If tissue is unavailable, subject may still enroll.
- 3.1.5 Subjects with prostate cancer must have documented prostate cancer progression within six months prior to screening with PSA progression defined as a minimum of two rising PSA levels ≥ 1 ; at least one week between each assessment with a baseline PSA value at screening of ≥ 2 ng/mL, including after first generation anti-androgen withdrawal.
- 3.1.6 Subjects with prostate cancer must have ongoing androgen deprivation with total serum testosterone < 50 ng/dL (or < 0.50 ng/mL or 1.73 nmol/L). If the subject is currently being treated with LHRH agonists (subjects who have not undergone an orchiectomy), this therapy must have been initiated at least 4 weeks prior to registration. This treatment must be continued throughout the study.
- 3.1.7 Subjects with non-prostate histologies must have RECIST 1.1-measurable cancer on computed tomography (CT) or magnetic resonance imaging (MRI) scans.
- 3.1.8 Subjects must have recovered to baseline or \leq grade 1 CTCAE v 4.03 from toxicities related to any prior treatments unless AE(s) are clinically non-significant and/or stable.
- 3.1.9 Patients must be ≥ 2 weeks from most recent systemic therapy or most recent radiation therapy.
- 3.1.10 Women of childbearing potential must have a negative serum or urine pregnancy test within 28 days prior to registration. Women of non-childbearing potential are

defined as those who have no uterus, ligation of the fallopian tubes, are naturally postmenopausal for at least 12 consecutive months or have undergone surgical removal of the ovaries.

3.1.11 Female and male subjects of reproductive potential must agree to use an adequate method of contraception starting with the first dose of study therapy through 5 months (for women) and 7 months (for men) after the last dose of study therapy.

3.1.12 Adequate organ and marrow function as defined below:

System	Laboratory Value
Hematological	
Absolute Neutrophil Count (ANC)	$\geq 1,000/\text{mm}^3$
Hemoglobin (Hgb)	$\geq 8 \text{ g/dL}$ with or without pRBC transfusion
Platelets (Plt)	$\geq 100,000/\text{mm}^3$
Renal	
Calculated or measured creatinine clearance	Serum creatinine $<3.0 \text{ mg/dL}$ or if elevated, a calculated estimated glomerular filtration rate (eGFR) of $\geq 30 \text{ mL/min/1.73 m}^2$.
Hepatic	
Total Bilirubin	$\leq 2.5 \times$ upper limit of normal (ULN) (patients with known Gilbert disease who have serum bilirubin $\leq 3 \times$ ULN may be enrolled)
Aspartate aminotransferase (AST)	$\leq 2.5 \times$ ULN
Alanine aminotransferase (ALT)	$\leq 2.5 \times$ ULN

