	
 6. Subjects with prostate cancer must have ongoing androgen deprivation with total serum testosterone < 50 ng/dL (or < 0.50 ng/mL or 1.73 nmol/L). If the subject is currently being treated with LHRH agonists (subjects who have not undergone an orchiectomy), this therapy must have been initiated at least 4 weeks prior to first dose of trial treatment. This treatment must be continued throughout the study. 7. Subjects with non-prostate histologies must have RECIST 1.1-measurable cancer on computed tomography (CT) or magnetic resonance imaging (MRI) scans. 8. Subjects must have recovered to baseline or ≤ grade 1 CTCAE v 4.03 from toxicities related to any prior treatments unless AE(s) are clinically non-significant and/or stable. 9. Patients must be ≥ 2 weeks from most recent systemic therapy or most recent radiation therapy. 10. Women of childbearing potential must have a negative serum or urine pregnancy test within 28 days prior to registration. Women of non-childbearing potential are defined as those who have no uterus, ligation of the fallopian tubes, are naturally postmenopausal for at least 12 consecutive months or have undergone surgical removal of the ovaries. 11. Female and male subjects of reproductive potential must agree to use an adequate method of contraception starting with the first dose of study therapy through 5 months (for women) and 7 months (for men) after the last dose of study therapy. 12. Adequate organ function with absolute neutrophil count (ANC) ≥ 1,000/mm³, hemoglobin ≥ 8.0 g/dL with or without pRBC transfusion; bilirubin/ALT/AST ≤ 2.5 x upper limit of normal (patients with known Gilbert disease who have serum bilirubin ≤3x ULN may be enrolled); serum creatinine <3.0 mg/dL or if elevated, a calculated estimated glomerular filtration rate (eGFR) of ≥30 mL/min/1.73 m².

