4.0 SUBJECT SCREENING AND REGISTRATION PROCEDURES

Patient registration for this trial will be centrally managed by the Coordinating Center of The University of Michigan Rogel Cancer Center as described below:

A potential study subject who has been screened for the trial and who has signed the Informed Consent document will be initially documented by the participating site on a Screening and Enrollment Log.

It is the responsibility of the local site investigator to determine patient eligibility prior to submitting patient registration request to the Coordinating Center. After patient eligibility has been determined, a copy of the completed Eligibility Worksheet together with all the pertinent de-identified source documents will be submitted by the requesting site to the Coordinating Center, by email to [contact].

The Multi-Site Coordinator (MSC) of the Coordinating Center will review the submitted documents and process the registration. Sites should inform the Multi-Site Coordinator of a potential registration by 5 p.m. on the day prior to registration. Same day registrations cannot be guaranteed.

An email will be sent by the MSC to the requesting site registrar to confirm patient registration and to provide the study identification number that has been assigned to the patient. In addition, a copy of the completed Eligibility Worksheet signed and dated by the MSC, will be sent back to the requesting site registrar.

Patients found to be ineligible for participation after being consented will be considered screen failures, and documented as such in a Screening and Enrollment Log. These patients will not have study identification number assigned to them, and will not receive study treatment.

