5.0 TREATMENT PLAN

5.1 Treatment Dosage and Administration

Protocol treatment must start within 14 business days of enrollment to the study.

- 5.1.1 In this study, Cohort A and Cohort B patients will start treatment with nivolumab dosed at 3 mg/kg IV and ipilimumab 1 mg/kg every 3 weeks for up to 4 doses. Cohort C patients will receive immunotherapy with nivolumab dosed at a flat dose of 480 mg IV every 4 weeks for up to 26 doses or 104 weeks.
- 5.1.2. Cohorts A and B maintenance immunotherapy with nivolumab dosed at a flat dose of 480 mg IV every 4 weeks will be continued for up to 23 doses or 92 weeks. Missed doses of 480 mg Nivolumab due to toxicity or general health condition will be skipped.

5.1.3 Total protocol therapy for all Cohorts will be up to 104 weeks during treatment. If disease progression or recurrence occurs during the follow-up phase, then per treating physician discretion, the patient may resume nivolumab 480 mg IV every 4 weeks until progression if tolerated with axial imaging as per protocol every, 12 weeks.

5.1.4 All study therapy will be administered on an outpatient basis.

Agent	Precautions	Dose	Route	Schedule	Cycle Length
Nivolumab (solution for injection) induction Cohort A and B only	Administer before other immunotherapy agents	3 mg/kg up to 4 doses	IV infusion over 30 minutes, +/- 10 minutes, with a sterile, nonpyrogenic, low protein binding 0.2 to 1.2 micrometer in-line filter. Follow with saline flush.	Day 1	3 weeks
Ipilimumab (solution for injection) induction Cohort A and B only	Administer 30 minutes after nivolumab.	1 mg/kg up to 4 doses	IV infusion over 90 minutes, +/- 10 minutes, through a non-pyrogenic, low protein-binding in-line filter. Separate IV line required.	Day 1	3 weeks
Nivolumab (solution for injection) maintenance After induction in Cohorts A and B; and throughout in Cohort C	Administer before other immunotherapy agents	480 mg up to 23 doses (92 weeks in Cohort A and B, and 104 weeks in Cohort C)	IV infusion over 30 minutes, +/- 10 minutes, with a sterile, nonpyrogenic, low protein binding 0.2 to 1.2 micrometer in-line filter. Follow with saline flush.	Day 1	4 weeks

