6.0 STUDY PROCEDURES

6.1 SCHEDULE OF ASSESSMENTS:

	Screening (within 28 days)	C1D1	C2D1	C3D1	C4D1	D1C5+	EOT¹²	Follow Up⁸
Informed Consent	X							
Review Eligibility Criteria	X							
Demographics, Height	X							
Prior and Concomitant Medications	X	X	X	X	X	X	X	
Review Adverse Events¹⁰	X	X	X	X	X	X	X	
Physical Examination, Vital Signs¹, Weight	X	X	X	X	X	X	X	
ECOG Performance Status	X	X	X	X	X	X	X	
Survival Status								X Q3m
Laboratory Assessments								
Pregnancy Test for WOBCP²	X							
CBC with diff, platelets³	X	X	X	X	X	X	X	
Comprehensive Metabolic Panel, including Alk Phos⁴	X	X	X	X	X	X	X	

	Screening (within 28 days)	C1D1	C2D1	C3D1	C4D1	D1C5+	EOT ¹²	Follow Up ⁸
LDH	X	X	X	X	X			
PSA¹¹	X	X	X	X	X	X	X	X
Testosterone¹¹	X				X		X	
TSH, free T3, free T4 (If Clinically Indicated: FSH, LH, ACTH)	X	X	X	X	X	X ⁶	X	
Therapy								
Cohorts A and B Nivolumab 3 mg/kg IV q3 wks for up to 4 doses¹³				X				
Cohorts A and B Ipilimumab 1 mg/kg IV q3 wks for up to 4 doses¹³				X				
Cohorts A and B Nivolumab 480 mg IV q4 wks for up to 23 doses¹³						X		
Cohort C Nivolumab 480 mg IV q4 wks¹⁴				X		X		
Imaging Tumor Assessments								
CT chest	X					X (q 12 wks)		
CT Abdomen/Pelvis or MRI Abdomen/Pelvis⁵	X					X (q 12 wks)		
Tc^{99m} Bone Scan (prostate only)	X					X (q 12 wks)		
QoL: BPI-SF and EORTC QLQ C30	X					X (q 12 wks)		
Correlatives								
Tumor Tissue Archival (CRPC preferred if available)	X							
Tumor Biopsy	X						X ⁷	
Research blood⁹		X	X	X		X (q 12 wks)	X	

1. Vital signs will include temperature, pulse, respirations, blood pressure; height will be obtained at screening only.
2. WOCBP: Women of child bearing potential; urine or serum pregnancy test.
3. CBC with diff includes total WBC, hemoglobin, hematocrit and differential of the WBC including absolute counts.
4. COMP or Comprehensive metabolic profile includes sodium, potassium, chloride, bicarbonate, BUN, creatinine, AST, ALT, alkaline phosphatase, total bilirubin.
5. With or without intravenous contrast, before or on associated visit. CT or MRI (preferred) brain with or without IV contrast if suspected or known brain metastases. Frequency of tumor assessments will be q12 weeks.
6. Every 42 calendar days ± 14 business days. May be delayed if infusion is not scheduled within the window.
7. Optional tissue biopsy collection at progression if subject consents; +/- 14 working days.
8. Follow up with phone call or with clinic visit.

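### Contraception is mandatory only from first dose although section 8.1 advises it from consent, and the only scheduled pregnancy test may be 46 to 48 days old at first dose if the registration anchor governs

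*Combined protocol and SAP*

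**What the plan says.** **Contraception.** Criterion 3.1.11, repeated as synopsis criterion 11, states that subjects of reproductive potential "must agree to use an adequate method of contraception starting with the first dose of study therapy". Section 3.0 makes this binding: "Subjects must meet all of the inclusion and exclusion criteria to be enrolled to the study". Section 8.1, under its special warnings, advises two methods acceptable to the investigator, one a condom, beginning when consent is given. The stop dates agree in both places: 5 months after last dose for women and 7 months for men.

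**Pregnancy test.** Criterion 3.1.10 and synopsis criterion 10 read: "Women of childbearing potential must have a negative serum or urine pregnancy test within 28 days prior to registration". Section 4.0 describes registration ("Patient registration for this trial will be centrally managed by the Coordinating Center") and gives no separate enrollment date. Section 5.1 adds: "Protocol treatment must start within 14 business days of enrollment to the study". In the 6.1 schedule, the row "Pregnancy Test for WOBCP" is marked once, in the column headed "Screening (within 28 days"; that heading names no reference date, and the table has no registration column. By contrast, "CBC with diff, platelets" and the metabolic panel are marked at both Screening and C1D1.

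**The concern.** There are two mismatches, and they compound.

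First, the rule a subject must accept in order to enter is weaker and starts later than the precaution the same protocol recommends. A woman who follows 8.1 is covered from consent. A woman who meets only the entry criterion has no required contraception between consent and first dose.

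Second, the one pregnancy test is timed against registration rather than dosing, and up to 14 business days may then pass. The schedule requires no second look at C1D1.

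Together, a woman could meet every mandatory criterion and receive nivolumab plus ipilimumab on a test more than six weeks old, with no contraception required by the eligibility text in between. Section 5.7.5, which takes a pregnant patient off study and sets the reporting timeline, operates only once the pregnancy is known, possibly after exposure.

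**Working it through.** The plan states no maximum test age, so there is no figure to reproduce. The check compares the contraception texts and then works out the test age.

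**Contraception, side by side**

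| | 3.1.11 and synopsis 11 | 8.1 |
|---|---|---|
| Force | entry requirement (via 3.0) | advice |
| Start | first dose | informed consent |
| Methods | one adequate method | two, one a condom |
| End | 5 months (women), 7 months (men) | the same |

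The two texts can be followed together, since 8.1 is the stricter. They differ in start date, number of methods and force, and no other section reconciles them.

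**Test age: inputs**

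- Test to registration: at most 28 days (3.1.10).
- Enrollment to first dose: at most 14 business days (5.1).
- Assumptions: registration and enrollment fall on the same day, that day is a weekday, and no public holiday intervenes.

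**Converting 14 business days.** Ten business days are two full weeks, or 14 calendar days. Four remain.

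- From a Monday, the four end on the Friday of the same week: 14 + 4 = 18 days.
- From Tuesday to Friday, the four cross a weekend: 14 + 4 + 2 = 20 days.

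**Maximum test age at C1D1** = days from test to registration + days from registration to first dose.

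- Registration anchor (3.1.10): 28 + 18 = 46 days, or 28 + 20 = 48 days.
- 6.1 heading counted back from C1D1: 28 days. A site must then satisfy both rules, and the tighter one governs.
- Difference between readings: 46 − 28 = 18 days to 48 − 28 = 20 days.

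**Sensitivity**

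- Counting the enrollment day as business day 1 leaves 13 further business days, or 17 to 19 calendar days: 28 + 17 = 45 to 28 + 19 = 47 days.
- One public holiday in the window makes it 15 weekdays, or 21 calendar days: 28 + 21 = 49 days. Under an assumed US federal holiday calendar for 2018 to 2030, the longest window is 25 days: 28 + 25 = 53 days.
- Applying the general window of ± 3 business days in the 6.1 note to the 28-day heading would give 31 to 33 days on the C1D1 reading.

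Every variant of the registration reading stays above six weeks (42 days).

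**The case against.** The strongest reply is that a sensible site would never reach the worst case. Section 8.1 already covers the interval before dosing for anyone who follows it. The screening column stands directly before C1D1, and baseline imaging sits in the same column. Section 7.3 limits baseline disease evaluations to four weeks before treatment start, which suggests that the column is counted back from dosing. On that reading the test is never older than 28 days. The harm also needs several conditions at once: the registration anchor governs, the test is done on the first permitted day, dosing falls on the last, and the advice in 8.1 is not followed. Few women are involved, and the consent form is not available to show what participants are told.

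Much of this stands as a limit on weight. The 46 to 48 days are maxima, and the documents give no distribution of actual intervals. It does not remove the inconsistency. Section 8.1 advises while 3.0 and 3.1.11 bind. Section 7.3 falls under the guidelines for measurable disease and does not clearly govern a pregnancy test. The only anchor actually stated for this test is registration. The ± 3 business day note applies unless something else is specified, and a stated 28-day limit is reasonably read as something else.

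**Conclusion.** The concern holds. The protocol gives two contraception rules and makes the weaker one binding. It also leaves the anchor of its only scheduled pregnancy test open between two readings whose maximum test ages are 28 days and 46 to 48 days. The larger figure assumes that registration is enrollment and that no holiday falls in the start window.

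The reach is small. The test-age problem concerns only women of childbearing potential, who can only be in Cohort B: at most 15 patients, and fewer once the definition in 3.1.10 is applied. The mismatch in method and start date covers all subjects of reproductive potential, but the interval before dosing matters only for these women. Sample size, type I error, power and analyses are untouched. This is a minor safety and consistency correction, worth making because it costs almost nothing. The conclusion concerns the protocol text alone; the consent form, Investigator's Brochure and label were not in the copy reviewed.

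**What to change.** 1. In 3.1.11 and synopsis criterion 11, start contraception at informed consent, as 8.1 already advises. Use the same method wording in all three places; whether that is one method or two is for the sponsor to decide.
2. In 3.1.10, synopsis criterion 10 and the 6.1 schedule, require a negative pregnancy test within 28 days before C1D1, repeated if the start is delayed beyond that. The 28-day figure is the plan's own; only its anchor becomes explicit. A repeat can be done with the laboratory tests already scheduled at C1D1, provided the result is known before dosing.

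This caps the test age at 28 days. Contraception from consent covers the remaining interval to the extent that it is followed. The cost is amendment wording in those places (and in 8.1 if its method wording changes), plus an occasional repeat urine or serum test for a few women in Cohort B.

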3.2 Exclusion Criteria

3.2.1 Prior treatment with anti-PD-1/PD-L1 and anti-CTLA-4 is NOT allowed. Prior intravesical BCG therapy is allowed.

3.2.2 Treatment with any investigational agent or on an interventional clinical trial within 28 days prior to registration on this protocol.

3.2.3 Prior or concurrent malignancy that has needed active interventional systemic therapy in the last 2 years. Adequately treated basal cell or squamous cell skin cancer, non muscle-invasive urothelial cancer, in situ cervical cancer, are permitted. For subjects in the non-prostate cancer cohort, localized or locally advanced prostate cancer definitively treated without recurrence or with biochemical recurrence only, or any other cancer fully treated or from which the subject has been disease-free for at least 2 years.

3.2.4 History or risk of any of the following significant autoimmune diseases are excluded, including but not limited to systemic lupus erythematosus, rheumatoid arthritis, inflammatory bowel disease, vascular thrombosis associated with antiphospholipid syndrome, Wegener's granulomatosis, Sjögren's syndrome, Bells' palsy, Guillain-Barre syndrome, multiple sclerosis, autoimmune thyroid disease, vasculitis, or glomerulonephritis. Vitiligo, mild psoriasis (topical therapy only) or hypothyroidism are allowed. No prior history of autoimmune pneumonitis allowed. Patients with previous drug-related or radiation therapy-associated pneumonitis, or other forms of pneumonitis, that has since resolved are allowed.

- 3.2.5 Need for systemic corticosteroids > 10mg prednisone daily or equivalent alternative steroid (except physiologic dose for adrenal replacement therapy) or other immunosuppressive agents (such as cyclosporine or methotrexate). Topical and inhaled corticosteroids are allowed if medically needed.
- 3.2.6 Any history of organ allografts.
- 3.2.7 Must not have known active hepatitis B, hepatitis C, or HIV seropositivity. Negative PCR suggests infection is not active or latent; however testing is not required in the absence of clinical suspicion.

4.0 SUBJECT SCREENING AND REGISTRATION PROCEDURES

Patient registration for this trial will be centrally managed by the Coordinating Center of The University of Michigan Rogel Cancer Center as described below:

A potential study subject who has been screened for the trial and who has signed the Informed Consent document will be initially documented by the participating site on a Screening and Enrollment Log.

It is the responsibility of the local site investigator to determine patient eligibility prior to submitting patient registration request to the Coordinating Center. After patient eligibility has been determined, a copy of the completed Eligibility Worksheet together with all the pertinent de-identified source documents will be submitted by the requesting site to the Coordinating Center, by email to [contact].

The Multi-Site Coordinator (MSC) of the Coordinating Center will review the submitted documents and process the registration. Sites should inform the Multi-Site Coordinator of a potential registration by 5 p.m. on the day prior to registration. Same day registrations cannot be guaranteed.

An email will be sent by the MSC to the requesting site registrar to confirm patient registration and to provide the study identification number that has been assigned to the patient. In addition, a copy of the completed Eligibility Worksheet signed and dated by the MSC, will be sent back to the requesting site registrar.

Patients found to be ineligible for participation after being consented will be considered screen failures, and documented as such in a Screening and Enrollment Log. These patients will not have study identification number assigned to them, and will not receive study treatment.

